### 6.4 STUDY INTERVENTION COMPLIANCE

Secondary Endpoint: Compliance will be measured as number of missed doses (self-reported) and defined by the detection of DHM at least 3 times above its limit of quantification via the LC-MS/MS methods at post-treatment in at least 80% of participants who complete the kava arm (e.g., 8/10).

### 6.5 CONCOMITANT THERAPY

---

#### 6.5.1 RESCUE MEDICINE

25 mg of Hydroxyzine every 6 hours

## 7 STUDY INTERVENTION DISCONTINUATION AND PARTICIPANT DISCONTINUATION/WITHDRAWAL

### 7.1 DISCONTINUATION OF STUDY INTERVENTION

This study will be stopped prior to its completion if: (1) the intervention is associated with adverse effects that call into question the safety of the intervention; (2) difficulty in study recruitment or retention will significantly impact the ability to evaluate the study endpoints; (3) any new information becomes available during the trial that necessitates stopping the trial; or (4) other situations occur that might warrant stopping the trial. If at any time during the study the participants are found to be at excessive risk, the study will be terminated. All key research personnel have completed the required human subjects training course. Key personnel include all individuals responsible for the design and conduct of the study.

### 7.2 PARTICIPANT DISCONTINUATION/WITHDRAWAL FROM THE STUDY

Study subjects will be informed that they are welcome to withdrawal or discontinue the study at any time should they feel this is not their best interest, does not meet their time availability, or for any other reason they see fit. Subjects will be asked to speak with the study coordinator or the investigator to indicate their request for withdrawal and all study related activity will stop.

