The study coordinator for the proposed project has 6 years of experience and will be trained in all study procedures. She will coordinate the screening of potential participants and will meet with [name] weekly to discuss study progress. [name], a gastroenterologist with expertise in hepatology and liver transplantation, will be responsible for overseeing the medical safety monitoring for this trial. He has extensive experience as a medical monitor for national clinical trials of multiple medications. He will communicate with [name] on a regular basis, and will also communicate any and all adverse events to the data safety monitoring board. He will interpret the results of the liver biochemistries (all results will be blinded to treatment condition) and will be responsible for referring participants to appropriate additional clinical evaluation and intervention if needed.

Effective screening will rule out active medical or psychiatric conditions, including supplement or medication use, chronic alcohol use, and evidence of pre-existing liver disease that may prevent someone from participating in the studies. Once the subject enters the study, an experienced research team will closely follow him or her. The research team has developed considerable expertise in monitoring the safety of subjects participating in research studies. An experienced research psychiatrist and the hepatologist is available 24 hours a day, 7 days a week. If at any point in the procedures symptoms become distressing or dangerous, subjects will be withdrawn from the study and, if necessary, treatment instituted.

This project will be conducted in compliance with research statutes outlined in the Health Insurance Portability and Accountability Act. Each participant will be assigned a unique identification number, and this number will be used to link all subsequent information collected. This file will be secured with password access, since it represents a direct link between the name and identification number of a participant. All paper files and data are kept in locked file cabinets to ensure confidentiality. The other procedures to ensure confidentiality follow the regulations and policies of the University of Florida and UF Health. Data file archival and back-up will be performed on a regular basis. The routine monitoring, maintenance, and quality control of the databases will be the responsibility of [name].

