*Emergence of Depressive or other Psychiatric Symptoms or Suicidality:* The research team will receive training in the rapid assessment and management of distress or emergence of psychiatric symptoms that may arise during the PK protocol. If a participant's status raises concern, [name] will offer a clinical evaluation and, when appropriate, participation in the study will be discontinued, and the participant will be referred for treatment according to clinical indication (hospitalization, partial hospitalization, other psychosocial interventions, pharmacotherapy, etc.). If a participant's psychiatric state worsens at any point such that they are no longer able to participate in the treatment, the participant will be withdrawn from the research protocol and referred for the appropriate treatment according to clinical indication. The same procedures apply to any participant who reports suicidal intent or plan or makes a suicide attempt at any point in the study. [name] is a licensed psychiatrist and will provide clinical oversight over assessments of suicidal ideation and safety.

*Management of psychiatric emergencies:* We believe that the risk of psychiatric emergencies occurring during the execution of this study is low, based on the pilot data and our findings of the patient population. However, should such an emergency arise (such as an acute decompensation, statement or demonstration of active suicidal ideation, violence, etc), we have procedures in place to ensure the safety of the participant and the staff.

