*Liver function abnormalities:* We will use a kava product that has removed the potentially liver toxic elements, flavokavain A and B, and has been rigorously tested for quality. However, we will nevertheless closely monitor serum liver biochemistries (AST, ALT, ALP, bilirubin (total, direct, and indirect) and albumin) at baseline, and at weeks 1, 4, 8 and 12. Although the timing of any potential liver toxicity with kava is not known, the timing of the few reported cases in the NIH liver tox database suggests that the onset of symptoms related to hepatotoxicity (including nausea, fatigue) is likely to be between 2 weeks and 12 weeks following initial ingestion. We will also encourage participants to contact the study team for any concerning symptoms that they may have for up to 6 months post-treatment to ensure that no delayed reactions, no matter how unlikely, are missed. We will carefully educate participants about symptoms to watch for throughout the study and following treatment.

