## 4 STUDY DESIGN

### 4.1 OVERALL DESIGN

**Aim:** To validate PRKACA reduction (primary outcome), cortisol, urinary TCE, and NA-5HT reductions (secondary outcomes) as biomarkers for kava-induced anxiolysis in GAD.

**Study design:** We will recruit and screen potential participants until we are able to randomize and enroll 26 individuals with GAD, with the expectation that 20 will complete the study (10 per arm) based on a conservative estimate of a 25% drop-out rate (the drop-out rate for our pilot study was 19%). We will build on our prior work with smokers by evaluating the utility of PRKACA as a biomarker for kava-induced anxiolysis among individuals with GAD. A one week double-blinded randomized, parallel, placebo-controlled trial of kava in GAD patients will be conducted. To minimize the risk of adverse events, particularly liver dysfunction, we will use flavokavain A/B-free kava in this study. Participants will be randomized, stratified by sex, to one of two conditions—placebo dosed three times a day or 75 mg of kava dosed three times a day. All pills will be taken with meals. Potential adverse effects will be evaluated via serum liver biochemistries and assessment of clinical symptoms in all participants at baseline, post treatment (day 7) and every 4 weeks for 12 weeks following discontinuation of treatment. Blood and urine for biomarker assessments will be collected at baseline and post treatment (day 7). CYP2D6 testing will be conducted at the screening visit to examine, at the end of the study, whether kava metabolism through this enzyme affects the biomarker responses.

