### 8.2 SAFETY AND OTHER ASSESSMENTS

Built upon our understanding of kava's hepatotoxic risk, a flavokavain A/B-free kava dietary supplement will be used in this trial, which is expected to reduce/eliminate kava's potential hepatotoxic risk. We will exclude individuals with elevated risk for hepatotoxicity, and will closely monitor liver function and other potential adverse events during and for 12 weeks following treatment.

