#### 9.4.4 SAFETY ANALYSES

First, we will rigorously analyze the kava product prior to use to ensure its consistent quality with no flavokavains A and B. Second, we have implemented stringent exclusion criteria and will provide education to the enrolled subjects to minimize potential drug-herb interactions. Third, we will monitor participants throughout the study and for 12 weeks following the end of treatment to ensure that any potential acute or delayed adverse effects are identified and addressed. Serum liver chemistries (AST, ALT, ALP, bilirubin (total, direct, and indirect) and albumin, Prothrombin Time and International Normalized Ratio) will be drawn at baseline, post treatment, and every 4 weeks following treatment up to 12 weeks. The adverse events checklist will be completed at each of these visits as well.

---

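### Withdrawal on request ends the 12-week liver follow-up planned for all participants, and the text on investigator withdrawal does not say whether those labs continue

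*Combined protocol and SAP*

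**What the plan says.** Three places govern leaving.

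- Section 7.2 covers withdrawal at the participant's request. The participant speaks to the coordinator or investigator "to indicate their request for withdrawal and all study related activity will stop". No exception is made for safety tests.
- Section 2.3.3 covers withdrawal by the team on two grounds. One is symptoms: "If at any point in the procedures symptoms become distressing or dangerous, subjects will be withdrawn from the study". The other is psychiatric worsening, for a person who is "no longer able to participate in the treatment, the participant will be withdrawn from the research protocol". Both mention treatment or referral. Neither mentions liver tests.
- Section 7.1 has a heading about discontinuing the intervention, but its body begins "This study will be stopped prior to its completion if" and lists grounds for ending the whole trial. It gives no rule for an individual who stops capsules and remains in the study.

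Three places govern liver follow-up.

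- Section 4.1 plans serum liver biochemistries and symptom assessment "in all participants at baseline, post treatment (day 7) and every 4 weeks for 12 weeks following discontinuation of treatment".
- Section 8.2 says the team "will closely monitor liver function and other potential adverse events during and for 12 weeks following treatment".
- Section 9.4.4 says "we will monitor participants throughout the study and for 12 weeks following the end of treatment".

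Section 2.3.3 also explains the length of follow-up: onset of symptoms related to hepatotoxicity "is likely to be between 2 weeks and 12 weeks following initial ingestion".

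**The concern.** Dosing lasts one week, and the protocol expects any liver symptoms to begin after that. The post-treatment panels are therefore its scheduled check for delayed kava liver injury. If the withdrawal text is followed as written, a person who has already taken kava can lose that check by leaving.

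For a requested withdrawal, section 7.2 and section 4.1 give opposite answers and nothing ranks them. For a withdrawal by the team, section 2.3.3 leaves the answer open. Because section 7.1 has no participant-level rule, staff have no defined status for someone who is off capsules but still attending safety visits.

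At stake are the individual's safety monitoring and a complete set of safety data on everyone dosed.

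**Working it through.** **Step 1. Tests lost per person.** The Schedule of Activities (1.3) puts CMPs after dosing at Day 7 and Weeks 4, 8 and 12, and PT/INR after dosing at Day 7 and Week 12. The onset window of 2 to 12 weeks from first ingestion is about Day 14 to Day 84. Day 7 falls before it. Days 28, 56 and 84 fall inside it.

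| Which text governs a person out by Day 7 | CMPs in window | PT/INR in window |
|---|---|---|
| 4.1 (labs for all) | 3 | 1 |
| 7.2, or 2.3.3 read as ending study visits | 0 | 0 |

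Someone out before the Day 7 visit has 0 of the 4 scheduled post-dose CMPs.

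**Step 2. How many people.** Sections 4.1 and 9.2 randomize 26 and expect 20 to complete. As a check on that figure, 20 / (1 − 0.25) = 26.7, so 26 is consistent with the stated 25% dropout to within rounding.

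- Expected non-completers: 26 − 20 = 6, and 6/26 = 23%.
- At the pilot's 19% dropout: 0.19 × 26 = 4.9, about 5.
- Ceiling on CMPs in the window, both arms, if all 6 were dosed and left by Day 7: 6 × 3 = 18 of 26 × 3 = 78, or 23%.
- Ceiling in the kava arm, if the 6 split equally: 3 × 3 = 9 of 13 × 3 = 39, or 23%.

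The documents give neither the timing nor the arm split of dropout, so these are upper figures.

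**Step 3. How many panels a fix could recover.** Only people who can be reached and agree will attend. With 3 kava leavers, of whom 0, 1, 2 or 3 attend, the recovered CMPs are 0, 3, 6 or 9 of 39 (0%, 8%, 15%, 23%). Section 7.3 expects 20% lost to follow-up, and 0.20 × 26 = 5.2. Its worked example of 2 does not match an enrolment of 26. Its definition covers people who no longer take part as well as people who cannot be reached, so the unreachable share of the 6 is unknown. It could be most of them.

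**Step 4. Adverse event recording.** Section 8.3.4 records new non-serious events for 7 days, and serious events for 30 days, after the last day of participation.

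- Withdrawn on Day 3, if that is the last day: 3 + 7 = Day 10 and 3 + 30 = Day 33.
- Followed to Week 12: 84 + 7 = Day 91 and 84 + 30 = Day 114.

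**Step 5. Expected liver cases.** Section 2.2 cites 0.3 to 1 case per million daily doses. Three kava leavers with at most 7 days each contribute 21 daily doses, so 21 × 0.3/1,000,000 = 0.0000063 to 21 × 1/1,000,000 = 0.000021 expected cases. Section 2.3.1 cautions that the true frequency is not known.

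**The case against.** **Stopping on request is a legitimate choice.** Section 10.1.1 lets participants withdraw consent at any time, and section 7.2 honours that. This stands. A reader might infer that the protocol is silent on every kind of leaver, but it is not: section 7.2 answers for requested withdrawal. The fault there is its conflict with section 4.1. The silence concerns withdrawals by the team.

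**Section 4.1 already covers people who stop capsules.** It can be read that way, and under that reading no panel is lost. Nothing says that it prevails over section 7.2 or over the withdrawal text in section 2.3.3, so the ambiguity remains.

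**Other safeguards exist.** Section 2.3.3 invites contact about symptoms for up to 6 months, provides round-the-clock access to a psychiatrist and hepatologist, and has a medical monitor who can refer participants. Section 8.3.4 follows recorded events to their outcome. Someone withdrawn for symptoms would normally have such an event. This largely stands and narrows the point: none of these safeguards schedules a blood test, so what is missing is mainly the planned labs in leavers who feel well.

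**The consent form may deal with this.** It is not among the pages available for review, so this cannot be checked either way. Whatever it says, the protocol sections would still disagree.

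**Stronger readings.** A reader might infer that 23% of liver panels will be lost, that leavers face higher liver risk, or that the trial's ability to detect liver toxicity is damaged. The documents support none of these. The 23% is a ceiling built on assumptions, no excess risk in leavers is shown, and the expected number of cases is close to zero either way.

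**Conclusion.** The concern holds as a minor point. Requested withdrawal under section 7.2 conflicts with the 12-week liver labs for all participants in section 4.1. Section 2.3.3 does not settle the matter for participants the team withdraws, and section 7.1 does not distinguish stopping treatment from leaving the study.

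The cost to one affected person is 3 CMPs and 1 PT/INR, on the assumption that they leave by Day 7 and the withdrawal text prevails. The number of such people runs from 0 to the 6 expected non-completers over both arms, and the number a wording change would help is smaller by however many cannot be reached or refuse. The point concerns individual safety monitoring and completeness of the safety data, and leaves the endpoints, power and alpha untouched.

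**What to change.** In section 7.2, with matching wording in the two withdrawal statements of section 2.3.3:

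- A dosed participant who stops capsules, or whom the investigator withdraws, comes off study treatment but remains in safety follow-up. They are offered whatever scheduled CMP, PT/INR and adverse event visits are still to come.
- A participant who asks to leave is asked separately whether they will attend those safety visits. All activity ends only if they decline.

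In section 8.3.4: for those who agree, the last safety visit counts as the last day of participation, so that event recording runs on from that visit.

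The decision on when to stop capsules can stay with the investigators and the participant.

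The cost is an amendment to the protocol and, if needed, to the consent form. The visits and tests are already scheduled, and section 5.5 already provides $25 per visit. An early leaver who attends all four remaining visits receives 4 × $25 = $100. If all 6 expected non-completers did so, the total would be 6 × $100 = $600. The practical downside is a few more attended visits.

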### 7.3 LOST TO FOLLOW-UP

NCCIH considers lost to follow-up as a research subject who was participating in the study at a certain point in time and subsequently missed two consecutive study visits and is unresponsive to study contact, or is no longer participating in study activities. The anticipated lost to follow-up rate for this study will be 20% of total enrollment (e.g., N=2).

## 8 STUDY ASSESSMENTS AND PROCEDURES

### 8.1 EFFICACY ASSESSMENTS

N/A

### 8.2 SAFETY AND OTHER ASSESSMENTS

Built upon our understanding of kava's hepatotoxic risk, a flavokavain A/B-free kava dietary supplement will be used in this trial, which is expected to reduce/eliminate kava's potential hepatotoxic risk. We will exclude individuals with elevated risk for hepatotoxicity, and will closely monitor liver function and other potential adverse events during and for 12 weeks following treatment.

### 8.3 ADVERSE EVENTS AND SERIOUS ADVERSE EVENTS

#### 8.3.1 DEFINITION OF ADVERSE EVENTS (AE)

An adverse event (AE) is any untoward medical occurrence in a subject during participation in the clinical study or with use of the experimental agent being studied. An adverse finding can include a sign, symptom, abnormal assessment (laboratory test value), or any combination of these regardless of relationship to participation in the study.

#### 8.3.2 DEFINITION OF SERIOUS ADVERSE EVENTS (SAE)

A serious adverse event (SAE) is one that meets one or more of the following criteria:

- Results in death
- Is life-threatening (places the subject at immediate risk of death from the event as it occurred)
- Results in inpatient hospitalization or prolongation of existing hospitalization
- Results in a persistent or significant disability or incapacity
- Results in a congenital anomaly or birth defect
- An important medical event that may not result in death, be life threatening, or require hospitalization may be considered an SAE when, based upon appropriate medical judgment, the event may jeopardize the subject and may require medical or surgical intervention to prevent one of the outcomes listed in this definition.

#### 8.3.3 CLASSIFICATION OF AN ADVERSE EVENT

Any undesirable and unintended (although not necessarily unexpected) effect occurring as a result of interventions, interactions, or collection of identifiable private information in research. In medical research, any untoward physical or psychological occurrence in research, including abnormal laboratory

finding, symptom, or disease temporally associated with the use of (although not necessarily related to) a medical treatment or procedure. Adverse events involving drugs are also referred to as adverse drug experiences. The PI will review and access for any adverse event classification in this study.

---

#### 8.3.3.1 SEVERITY OF EVENT

The following scale will be used to grade adverse events:

1. Mild: no intervention required; no impact on activities of daily living (ADL)
2. Moderate: minimal, local, or non-invasive intervention indicated; moderate impact on ADL
3. Severe: significant symptoms requiring invasive intervention; subject seeks medical attention, needs major assistance with ADL

---

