### 8.3.8 EVENTS OF SPECIAL INTEREST

None

---

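### The only severity scale has no laboratory criterion, so an asymptomatic liver-test rise of any size is mild unless an intervention is judged indicated

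*Combined protocol and SAP*

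**What the plan says.** Section 8.3.1 brings laboratory results within the definition of an adverse event: "An adverse finding can include a sign, symptom, abnormal assessment (laboratory test value), or any combination of these". Section 8.3.3 repeats that abnormal laboratory findings count.

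Section 8.3.3.1 then sets one scale for everything: "The following scale will be used to grade adverse events". The three levels are:

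- "Mild: no intervention required; no impact on activities of daily living (ADL"
- "Moderate: minimal, local, or non-invasive intervention indicated; moderate impact on ADL"
- "Severe: significant symptoms requiring invasive intervention; subject seeks medical attention, needs major assistance with ADL"

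Section 8.3.8, headed "EVENTS OF SPECIAL INTEREST", has the single entry None.

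Section 8.2 says that the team "will closely monitor liver function and other potential adverse events during and for 12 weeks following treatment". Section 2.3.1 names acute liver injury, up to fulminant hepatic failure, among the possible risks of kava. The synopsis (section 1.1) gives delayed rare events, liver toxicity in particular, as the purpose of the 12-week follow-up. Section 9.4.4 (Safety Analyses) describes product testing, exclusions and the timing of the liver tests, but no summary of the results.

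**The concern.** The expected course of a drug-related liver signal in a trial like this is a change in laboratory values before any symptom. Such a change is an adverse event under section 8.3.1, so it must receive a grade, and the only grades available do not look at the laboratory value. A trivial rise and a very large one, both without symptoms and both judged to need no intervention, would enter the record under the same label.

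Two things are at stake. First, the adverse-event record would understate the size of a liver abnormality, which is the finding that the follow-up is mainly there to detect. Second, section 8.3.3.3 makes severity one of three grounds for calling an event unexpected, so a label of mild could bear on that decision. Neither the special-interest section nor the safety-analysis section makes up for this, since one is empty and the other plans no presentation of liver results by arm.

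**Working it through.** The plan states no enzyme cut-off and no expected rate of liver-test rises, so there is no figure to reproduce. The check is to apply the scale literally to one case and then look for a rule elsewhere that would change the answer.

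**Step 1. Is the event graded on this scale?** Yes. Section 8.3.1 makes it an adverse event, and section 8.3.3.1 applies its scale to adverse events without exception.

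**Step 2. Which grade does an asymptomatic liver-test rise with no effect on daily function receive?**

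| Situation | Grade as written | Does size matter? |
|---|---|---|
| No intervention required | Mild | No |
| Non-invasive intervention judged indicated, semicolon in the moderate grade read as *or* | Moderate | No |
| Same, semicolon read as *and* | None fits: mild fails on intervention, moderate fails on daily function | No |
| Severe | Not reached, because the grade opens with significant symptoms requiring invasive intervention | No |

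One qualification applies to the last row. If each clause of the severe grade were detached and taken as sufficient alone, seeking medical attention could place an asymptomatic participant there. I do not read it that way, because symptoms are the leading criterion. Even on that reading the grade would depend on behaviour and not on the laboratory value.

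**Step 3. Does another section supply a laboratory grade or a liver threshold?**

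- Section 5.2 excludes clinically significant elevations at entry, by judgement, with no number.
- Section 2.3.3 has a hepatologist, as medical monitor, read the liver results blinded to arm and refer participants where needed. It gives no grade.
- Section 8.3.2 allows an important medical event to be called serious on medical judgement. That concerns seriousness, not severity.
- Section 8.3.7 has abnormal liver values discussed with the participant.
- Section 10.1.6 places a hepatologist on the monitoring board.
- Section 10.1.7 lists liver function as its own item in the monitor's reports, in aggregate and not by arm.
- Section 3 lists liver function tests as an endpoint, under the heading Compliance, with no analysis attached.

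None of these ranks a liver abnormality by size in the adverse-event record.

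**Step 4. How much data is involved?** The Schedule of Activities (section 1.3) has a metabolic panel at weeks 1, 4, 8 and 12, so 4 per participant after baseline. With 26 randomised, 4 × 26 = 104 scheduled panels. The 20 expected completers would contribute 4 × 20 = 80. These count panels on which a rise could be seen. They do not estimate how many events would be misgraded.

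**The case against.** The strongest reply is that the grade is not what protects participants or informs the monitors. A hepatologist reads the liver results, another sits on the board, and judgement can make a laboratory event serious. Expedited reporting under section 8.3.6 turns on seriousness, expectedness and relatedness rather than on the three-level grade. Liver function also reaches the monitor as a separate item (section 10.1.7). All of this stands. A reader might infer from the scale that liver safety is unmonitored, or that a large asymptomatic rise could never be reported as serious; the documents support neither inference.

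A reader might also infer that severity tables sent to the board or funder would conceal a difference between kava and placebo. That does not follow. Sections 8.3.5, 8.3.6 and 10.1.6 promise lists and summaries of adverse events and do not mention severity tables. Section 10.1.7 keeps the report tables aggregate, so no difference between arms would appear in them under any scale. The numeric liver values will also exist at the end of the trial whatever grade was recorded.

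It may be said, too, that an entry in section 8.3.8 is only a label, since no procedure is tied to it. That is partly right. The substantive gap is the missing grade together with the missing final table, and the empty section 8.3.8 matters mainly because it sits badly with sections 2.3.1, 2.3.3 and 9.4.4.

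Finally, section 8.3.3.3 does not say that its severity is the grade from section 8.3.3.1, so the effect on expectedness is possible rather than certain.

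What the reply leaves untouched is that the safeguards concern individual care and seriousness. None of them provides a consistent grade, and section 8.3.3 leaves classification of adverse events to the principal investigator.

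**Conclusion.** The point holds in this limited form. The plan states a grading rule that, applied as written, calls an asymptomatic liver-test rise of any size mild unless an intervention is judged indicated, and never severe while the participant has no symptoms. Nothing elsewhere corrects the grade. Section 8.3.8 is empty and section 9.4.4 plans no presentation by arm, although liver injury is the main named risk.

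Its size cannot be put as a rate. The 104 scheduled panels are the most that could be affected and are not an effect. The reach of the defect is also bounded: it affects the recorded severity, possibly the expectedness decision, and the final safety account, but not the existence of monitoring. Nor is liver toxicity the sole purpose of the follow-up, as a reader might conclude; the synopsis and section 9.4.4 both describe a wider search for delayed events, and the synopsis singles out liver toxicity within it.

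The conclusion assumes that the scale is applied literally and that significant symptoms are a necessary part of the severe grade. It should be corrected, because the rule gives a misleading label for the trial's main safety outcome and the correction uses data already being collected.

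**What to change.** - **Section 8.3.3.1:** add that liver-test abnormalities are graded on a published laboratory grading scale, chosen by the trial's hepatologist and named in the protocol. Keep the present scale for clinical events. The choice of scale and any thresholds are for the clinicians.
- **Section 8.3.8:** replace the entry None with liver-test abnormality or liver injury, so that it agrees with sections 2.3.1, 2.3.3 and 9.4.4.
- **Section 9.4.4:** add one descriptive table, by arm, of each participant's peak post-baseline value and grade for each liver test. Produce it at the final analysis only, and leave the monitoring reports aggregate as section 10.1.7 requires.

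The cost is protocol wording and one table, with no new visits or samples. The downside is that some events will be graded higher than under the present scale. No change to clinical management is proposed.
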